Patients with CF, carrying 2 severe mutations referred to Class I and II, i.e. mutations associated with more severe LA deficiency and more severe clinical symptoms, (like delF508, 394delTT) are included after informed consent. The reason for including only those with clinically more severe phenotype is that those have pancreatic insufficiency and also other symptoms more expressively related to genotype (see above). Exclusion criteria will be pregnancy and transplantation and age above 15 and below 5 years (due to pulmonary function tests) and severe liver disease (cirrhosis, portal hypertension). The patients shall not have taken any lipid supplements for 2 months before inclusion and not be treated with any modulators (like Orkambi, Trikafta).

The patients will keep to their ordinary treatment of PERT and vitamins and that for the pulmonary symptoms and infections. No special dietary recommendations will be given, but PERT might be increased, when the supplement is given and that shall be registered. Number of pulmonary exacerbations and type of treatment, including antibiotics, are registered and also compared with the year before the study.

Sample size

A sample of 84 patients (42 per group) will ensure that a two-sided test with α =0.05 has 80% power to detect a 0.5 mean difference in 1-year change in weight-

for-age Z-score, assuming a pooled standard deviation of 0.8. This last figure has been obtained from a previous intervention study on cystic fibrosis patients (Alicandro et al. 2013). Since we expect a withdrawal rate of close to 10%, we planned to enroll 90 patients (45 per groups). The patients and caregivers will be informed by oral and written information and included after informed consent. The study is approved by local Ethic Committees and by the one at Karolinska Institutet and the study is performed according to the Helsinki Declaration.

Design

The study is designed as a double-blind randomized clinical trial

The patients will be randomized to either

- treatment A: linoleic acid (12 g for children 5-15 years) + 600 mg algeal DHA
- treatment B: oleic acid (12 g for children 5-15 years) + 600 mg algeal DHA

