The fatty acids will be given daily for 12 months, in vials containing an emulsion of totally 20 ml (provided by AKK Company, Karlshamn, Sweden and Copenhagen Denmark, packed by WinterMedic, Odense, Denmark), which can be mixed with milk, juice, sour cream, porridge or any similar feeding at breakfast time. Some extra enzymes may be added.

The treatment will last 12 months, starting and ending at time of the yearly check up of the patients. Half the number of patients will be randomly allocated to receive either treatment A or B. An independent researcher (not involved in the study) will generate the allocation sequence at each center. This will reduce small differences in local treatment policy. The vials with supplementation will only be coded (black or white capsula) so neither patient nor caregivers or staff in charge will be informed by the type of supplementation.

Primary Outcome

- BMI Z-score, weight-Z-score

Secondary outcomes

- Height Z-score
- FEV1 (% of predicted) and oxygen saturation
- Exacerbations and infectious parameters compared to year before.
- Plasma phospholipid fatty acid profile.
- Plasma concentration of IGF-I

Explanatory outcomes

- Bone mineral density
- Lean body mass and fat mass.
- Liver function tests
- Lipid mediators (like eicosanoids and docosanoids)
- Cytokines
- 8-iso-prostane
- Sweat sodium and chloride concentrations
- Renal sodium excretion
- Resting energy expenditure
- Intestinal function (fecal calprotectin and fat absorption coefficient)
- Oral glucose tolerance with insulin determination.

METHODS

Patients will be screened for enrollment and will be allocated to one of the treatment at baseline visit. Follow-up visits will be scheduled at 6 and 12 months after treatment allocation. Some measures, like fat absorption coefficient and calprotectin and resting energy expenditure, exhaled NO and ergometer test will not be performed in all patients due to limited capacity at some centres. The study procedures are summarized in table 1.

Table 1. Outline of study procedures

	Baseline visit: Screening and allocation	+6 months	+12 months
Anthropometry	X	X	X
DXA	X		X
FFQ	X	X	X
24-h dietary recall	X	X	X
Pulmonary function	X		X
Blood sample	X	X	X
F-Calprotectin	X		X
Urine sample	X		X
Ergometer test with oxygen saturation	X		X
Oral glucose tolerance	X		X
Indirect calorimetry	X		X
Sweat test	X		X
Compliance to treatment	X	X	X
CF Questionnaire	X	X	X

1. *Anthropometry.*

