Height and weight are controlled with the same equipment for each patient at respective centre and at each scheduled visit (baseline, 6 and 12 months after allocation). Z-scores of weight, height and BMI will be computed using WHO as growth standard. DXA is performed at start and after 12 months period for determination of bone mineral content and density, lean body mass and fat mass.

1. *Food registration.*

- Food frequency questionnaire (FFQ) will be performed at start and each scheduled visit, mainly used for calculation of energy intake and intake of fat and fatty acids (validated questionnaire Eriksson S et al. 2010). Since the products are different in different countries the FFQ form can only suggest **type** of products to be evaluated, complemented by the local dietician. The reason to include these registrations is to individually make a comparison with intake at start and end of study possible, checking that not major changes have occurred in diet, which can influence the results.
- 24-hour recall will be performed at start, 6 months and 12 months after allocation as a complement to FFQ for portion size, type of products etc.

3. *Pulmonary function.*

- Routine pulmonary function (FEV1) at each clinical visit
- Full spirometry at start and end of treatment
- Exhaled NO (if available)
- Ergometer test at start and end
- Oxygen saturation (ear-tip).

4. *Biochemistry.*

- Routine blood biochemistry (fasting) at start and end of treatment period, including Hb, platelets, white blood cell count and differential count, ASAT, ALAT, alkaline phosphatase, GGT, PK, total and conjugated bilirubin, bile acids, cholesterol, lipoproteins, triglycerides, urea, creatinine, glomerulus filtration rate. Ig-G, CRP, sedimentation rate.

- 1 ml serum/plasma for later analyses (to freezer divided in 4 tubes for later analyses of lipid mediators at KI).
- 0,5 ml for IGF-I analysis (to freezer for later analysis in Sweden)
- 0.5 ml plasma for cytokines (to freezer for sending to Stockholm for analyses (OLINK, Uppsala, Sweden).
- 0.5 ml plasma for analyses of phospholipid fatty acids (to freezer for later analysis in Poznan or Stockholm).
- Urine sample for routine tests, incl sodium and creatinine concentrations.

5. *Intestinal function*

- F-Calprotectin at start and after 12 months (in freezer for later analyses at one center)
- Fat absorption at start and 12 months. Three day dietary recording and feces

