Sampling. Mixture in local laboratory with freezing of an aliquote for later transport to Poznan

6. *Metabolic tests*

- Urine sample for 8-isoprostanate and lipid mediators as eicosanoids, docosanoids and linoleic acid metabolites (directly to freezer -80 each sample in 2 x 8 ml and in 4 x 2 ml) for later analyses in Stockholm.
- Indirect calorimetry at start and after 12 months (if available in the hospital).
- Sweat test at start and after 12 months. **Both sodium** and chloride analyses.
- Oral glucose tolerance test.

7. *Quality of life.*

Quality of life will be assessed through the CF Questionnaire Revised (CFQ), a disease-specific tool that measures health-related quality of life in patients with

CF. There are different versions of the questionnaire: two for children over 6 years, one to be completed by the child and one to be completed by parent (CFQ Child and CFQ-Parent, respectively).

8. Compliance with the treatment

Compliance with the treatment will be evaluated by monthly contact with the study coordinator of respective centre, when not used vials will be registered and new supplied. The patients are asked to make a dairy over the daily intake also reported monthly to the coordinator. Extent of physical activity shall be notified.

9. Statistics

All data will be collected in identical Excel files and analysed in one center at end study.

The main analysis will be carried out on the intention-to-treat population defined as all randomized patients. We will also conduct a secondary analysis on the per-protocol population excluding patients not receiving the allocated treatment for more than 2 months.

Between-treatment differences in the primary outcome across time points will be evaluated by fitting random intercept linear mixed-effects models. Mixed effects model can account for intra-correlated repeated measures on the same subjects and accommodate missing data due to dropouts. The models will include the z-score of BMI as response variable, treatment, time and time x treatment interaction as independent variables. The model coefficients for the time x treatment interaction will be considered an estimate of the treatment effect on changes in the study outcome. Time will be included in the model as categorical variable with the following categories: baseline (pre-treatment), +6 months and +12 months from treatment allocation.

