Secondary and explanatory outcomes will be compared across treatment groups using the paired t-test for normally distributed variables, otherwise the non-parametric Wilcoxon signed-rank test for dependent samples will be used.

A stratified analysis by sex will be performed.

RISK-BENEFIT

There will be no adverse effects to expect of this treatment , since the control group will have the same treatment as offered generally to patients, i.e. extra calories. The extra LA will not exceed the general intake in US (Choque et al 2014). Both groups get similar amount of omega-3 fatty acids; dose in agreement with general recommendations. The extra burden of investigations is small since the patients always have more extensive investigations at the yearly checkup.

IMPORTANCE

If clinical status is improved the patients in both groups will be asked for the possibility to continue with Group A therapy for one further year (requires new ethical applications). Furthermore, good result would indicate a multicenter study for treatment from diagnosis in countries with neonatal screening, which would be extremely important since many of the symptoms start early and especially the supply of high caloric diet gives many problems in patients and parents, and unsatisfying results, It can also have the potential to be a cheap complement to modern expensive drug treatment.

A special benefit for individuals and society would be if this simple, cheap and non hazardous treatment can reduce the enormous costs of the modern drug treatment, which is further not always available.

References:

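### Secondary and explanatory outcomes are to be compared between two independent arms with paired tests, so no linoleic versus oleic acid test is defined for them

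*Protocol*

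**What the plan says.** The rule for every non-primary outcome is one sentence in Protocol section 9 (Statistics): "Secondary and explanatory outcomes will be compared across treatment groups using the paired t-test for normally distributed variables". For variables that are not normally distributed, the same sentence names the Wilcoxon signed-rank test and describes it as a test for dependent samples. Section 9 of the SAP uses the same words.

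The Design section describes a parallel-group trial: "Half the number of patients will be randomly allocated to receive either treatment A or B". No crossover, matching or pairing rule appears in either document.

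The primary outcome is handled differently. A random-intercept mixed model is fitted to BMI Z-score, and "The model coefficients for the time x treatment interaction will be considered an estimate of the treatment effect on changes in the study outcome". That is a proper between-arm contrast, but it is specified for the primary outcome only.

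**The concern.** Paired tests need two measurements that belong together. Here the LA and OA children are different, unmatched people. The plan names two dependent-sample tests and adds that the samples are dependent, which makes a simple typing slip less likely.

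The sentence is the only analysis rule for all 5 secondary bullets (height Z-score; FEV1 and oxygen saturation; exacerbations and infectious parameters; plasma phospholipid fatty acids; IGF-I) and all 11 explanatory bullets. The stated aim covers clinical status and metabolism. The metabolic half of that aim, and the lung, infection and height results, therefore have no defined LA versus OA test.

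An analyst would have to improvise one, possibly after seeing the data. Alternatively, the analyst might run before/after tests in each arm and conclude that LA works because only the LA arm reached significance. The plan does not state that decision rule, but separate before/after tests would supply no between-arm test to use instead.

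**Working it through.** **Inputs.** From Protocol, Sample size: 42 analysed per arm, two-sided α = 0.05, 80% power, difference 0.5, SD 0.8, withdrawal close to 10%, 45 enrolled per arm. The documents give no SD or expected change for the secondary outcomes, so shared change is varied as an assumption, in units of the SD of within-patient change.

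**1. The plan's own sample size treats the arms as independent.** The normal formula n = 2(1.96 + 0.84)² × (0.8/0.5)² gives 40.2, so 41 per arm. The exact two-sample t-test gives 41.17, so 42 per arm, matching the stated 84. Power at 42 per arm is 80.8%. A paired test at 0.5/0.8 = 0.625 SD would need only 23 subjects.

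**2. Reading one: LA and OA children paired arbitrarily.**
- In simulation with 42 per arm, type I error is 4.9% paired and 4.9% unpaired. Power at 0.625 SD is 79.9% and 80.7%. There is no inflation and almost no loss of power.
- The p-value depends on row order. Re-ordering one arm changes the significance verdict in 1.9% of trials at zero difference, 6.6% at 0.5 SD and 4.8% at 0.625 SD.
- In a borderline data set built to have independent-samples p = 0.05, the paired p ran from 0.022 to 0.088 over the central 95% of orderings, and 42% of orderings fell below 0.05.
- The test needs equal numbers. With completers Binomial(45, 0.90) in each arm, P(equal) = Σ P(k)² = 14.1%, and the mean gap is 2.2 patients. At 5% and 15% withdrawal, P(equal) is 19.8% and 11.8%. Otherwise some patients must be left out.

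**3. Reading two: before/after within each arm, no true LA–OA difference.** Let δ be the shared change in SD units. The chance that one arm is significant is p = P(|T| > 2.02), where T is noncentral t with 41 df and noncentrality δ√42. The arms are independent, so exactly one is significant with probability 2p(1 − p), and only the LA arm with p(1 − p). For δ = 0.3, noncentrality is 0.3 × 6.48 = 1.94 and p = 0.476, so 2 × 0.476 × 0.524 = 0.499.

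| Shared change δ (SD) | One given arm significant | Exactly one arm significant | Only LA significant |
|---|---|---|---|
| 0 | 5.0% | 9.5% | 4.8% |
| 0.1 | 9.7% | 17.5% | 8.8% |
| 0.2 | 24.4% | 36.9% | 18.5% |
| 0.3 | 47.6% | 49.9% | 24.9% |
| 0.4 | 71.6% | 40.7% | 20.3% |
| 0.5 | 88.6% | 20.3% | 10.1% |

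The risk rises and then falls, because at large shared change both arms become significant. The last column counts either direction. In the direction of the shared change it is 2.4% at δ = 0 (either direction serving as favourable), 8.3% at 0.1, and essentially unchanged from 0.2 upward. A two-sample t-test on change, simulated under the same null, rejects in 5.0%, 4.9% and 5.1% of trials at δ = 0, 0.2 and 0.5.

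**4. Reading two with a true difference of 0.625 SD** (the plan's primary effect size, used for illustration). At a shared change of 0.5 SD, both arms are significant in 89% of trials and only LA in 11%. A between-arm test has 81% power. Before/after testing can therefore also hide a real effect.

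**The case against.** The strongest case for leniency is that the contrast is stated correctly (across treatment groups) and only the test names are wrong. The primary analysis is sound, the sample size was computed for independent arms, and no confirmatory claim is attached to these outcomes. Arbitrary pairing is nearly harmless on average, and the p = 0.05 example is a boundary case. The before/after problem depends on shared change, for which the documents give no figure. At zero shared change, a favourable LA-only result occurs in 2.4% of trials, so false LA claims are not inflated there.

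Most of this is fair as to size. Shared drift is less plausible for FEV1 as a percentage of predicted and for height, since "Z-scores of weight, height and BMI will be computed using WHO as growth standard". It is more plausible elsewhere. Bone mineral content and lean mass rise as children grow. Both arms receive 600 mg DHA, and the protocol's Background reports that earlier omega-3 trials markedly raised plasma omega-3, so the phospholipid profile may well move in both arms.

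It can also be said that the authors meant before/after comparisons. The bullet "Exacerbations and infectious parameters compared to year before" supports that for exacerbations and infectious parameters only. Baseline to 12 months is not the only within-patient pair either, since Table 1 schedules anthropometry and blood samples at 6 months too. Neither point helps, because no within-patient pairing compares LA with OA.

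The objections limit the numerical consequences but leave the defect in place: no other sentence supplies a between-arm test for these outcomes.

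**Conclusion.** The concern holds, and the sentence must be corrected before analysis. The specified tests do not fit the design, and on neither reading do the 5 secondary and 11 explanatory bullets have a usable LA versus OA test. The primary BMI Z-score model is not affected.

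That conclusion rests on the text alone. The size of the harm rests on assumptions. Under arbitrary pairing the cost is an arbitrary p-value and discarded patients, not a raised error rate. Under before/after testing, the chance of a misleading one-arm-only result with no true difference depends on the unknown shared change, and peaks near 50% (about 25% for LA only) at around 0.3 SD with 42 per arm. Those figures become false conclusions only if the reader infers a treatment effect from which arm is significant.

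**What to change.** Replace the sentence in section 9 of both documents.

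- **Minimum repair:** a two-sample t-test, or a Wilcoxon rank-sum test for non-normal variables, comparing change from baseline between the arms.
- **Preferred wording:** *Continuous secondary and explanatory outcomes will be compared between arms by ANCOVA of the 12-month value adjusted for baseline, or by the primary mixed model where 6-month data exist, reporting the LA minus OA difference with 95% CI; skewed markers will be log-transformed or ranked.*
- **Exacerbations (a desirable addition):** a count model such as negative binomial, with treatment, the prior-year count as covariate and follow-up time as offset.
- **Within-arm before/after tests:** keep if wanted, labelled descriptive only.

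Centre adjustment is optional and may be impractical for measures that "will not be performed in all patients due to limited capacity at some centres".

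The cost is one sentence in each document, or two if the count model is added. Baseline, 12-month and prior-year exacerbation data are already planned, and the sample size of 84 does not change.

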## 9. Statistics

All data will be collected in identical Excel files and analysed in one center at end study.

The main analysis will be carried out on the intention-to-treat population defined as all randomized patients. We will also conduct a secondary analysis on the per-protocol population excluding patients not receiving the allocated treatment for more than 2 months.

Between-treatment differences in the primary outcome across time points will be evaluated by fitting random intercept linear mixed-effects models. Mixed effects model can account for intra-correlated repeated measures on the same subjects and accommodate missing data due to dropouts. The models will include the z-score of BMI as response variable, treatment, time and time x treatment interaction as independent variables. The model coefficients for the time x treatment interaction will be considered an estimate of the treatment effect on changes in the study outcome. Time will be included in the model as categorical variable with the following categories: baseline (pre-treatment), +6 months and +12 months from treatment allocation.

Secondary and explanatory outcomes will be compared across treatment groups using the paired t-test for normally distributed variables, otherwise the non-parametric Wilcoxon signed-rank test for dependent samples will be used.

A stratified analysis by sex will be performed.

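### Secondary and explanatory outcomes: the test is picked by an undefined normality judgement, the collected baseline value goes unused, and no LA versus OA estimate with confidence interval is planned

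*Protocol*

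**What the plan says.** Section 9 (Statistics) of the protocol and of the SAP carry the same sentence. It opens "Secondary and explanatory outcomes will be compared across treatment groups" and then names the method: "the paired t-test for normally distributed variables, otherwise the non-parametric Wilcoxon signed-rank test for dependent samples will be used". The SAP copy ends identically: "otherwise the non-parametric Wilcoxon signed-rank test for dependent samples will be used".

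Neither document says how normality is judged, or whether on raw values, changes or residuals. Neither plans a transformation, a baseline adjustment or an effect estimate with interval for these outcomes. Only the primary outcome has a model, in which the treatment-by-time coefficient is the effect.

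The protocol's list of explanatory outcomes includes "Lipid mediators (like eicosanoids and docosanoids", cytokines, 8-iso-prostane, liver tests and "Intestinal function (fecal calprotectin and fat absorption coefficient". Its Table 1 schedules blood, urine, calprotectin and lung function at both baseline and 12 months, so a baseline value is normally available. The Methods section adds that some measures, calprotectin among them, will not be done in every child.

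**The concern.** The rule fixes neither the estimand nor the method. Whether an outcome gets a t-test or a rank test depends on an undefined reading of the trial's own data. The baseline measurement, which in a randomised comparison is the cheapest source of precision, has no stated role. The result would be a p-value with no planned statement of how far LA and OA differ.

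This matters because the protocol's rationale rests partly on LA lowering arachidonic acid and the mediators derived from it. The size of that effect, with its uncertainty, is what a reader will want. Concentration markers of this kind are often right-skewed and tend to change by a ratio. The documents do not say so; that is an assumption here.

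**Working it through.** **The plan's own figure.** The only sample size stated is for growth: "a two-sided test with α =0.05 has 80% power" and is sized "to detect a 0.5 mean difference in 1-year change" in weight-for-age Z-score, with SD 0.8. The normal approximation gives n = 2 × (1.96 + 0.8416)² × 0.8² / 0.5² = 40.2, so 41 per arm. With the t distribution, power is 79.8% at 41 and 80.8% at 42. The plan's 42 per arm reproduces. No power is stated for any secondary or explanatory outcome; 42 per arm is carried forward as the evaluable number.

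**Assumed inputs (none in the documents).** Log-normal marker; true ratio 0.65, so the log effect is |ln 0.65| = 0.431; log SD s = 0.6, 0.8, 1.0; baseline to 12-month log correlation r = 0.4, 0.6. The tests are taken in independent-sample form, since the paired form cannot compare two arms.

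**Reading 1: 12-month values are compared.**
- Baseline-adjusted log model: SE = s × √[(1 − r²) × 2/42]; power ≈ Φ(0.431/SE − 1.96).
- t-test on log 12-month values: SE = s × √(2/42), same power formula.
- Rank-sum on 12-month values: as the t-test, with the signal multiplied by √(3/π) = 0.977, its large-sample efficiency when the log values are normal.

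Example, s = 0.6, r = 0.4. Adjusted: SE = 0.6 × √(0.84 × 2/42) = 0.120, 0.431/0.120 = 3.59, Φ(1.63) = 94.8%. Rank-sum: SE = 0.6 × 0.2182 = 0.131, 3.29 × 0.977 = 3.215, Φ(1.255) = 89.5%. The gap is 5.3 points.

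| s | r | Adjusted log model | t-test, log 12-month | Rank-sum, 12-month | Adjusted minus rank-sum |
|---|---|---|---|---|---|
| 0.6 | 0.4 | 94.8% | 90.8% | 89.5% | 5.3 |
| 0.6 | 0.6 | 98.4% | 90.8% | 89.5% | 8.9 |
| 0.8 | 0.4 | 76.8% | 69.4% | 67.4% | 9.4 |
| 0.8 | 0.6 | 87.0% | 69.4% | 67.4% | 19.5 |
| 1.0 | 0.4 | 57.7% | 50.6% | 48.8% | 8.9 |
| 1.0 | 0.6 | 69.4% | 50.6% | 48.8% | 20.6 |

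The gap is about 5 to 21 points; simulation gives the same range. Ranking itself costs only 1 to 2 points (fourth column minus fifth). The rest is the missing baseline.

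**Reading 2: raw change is compared.** Simulation, 4000 runs per setting. The rule is represented as a t-test if Shapiro-Wilk p > 0.05 in both arms, otherwise rank-sum.

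| s | r | Gated rule, raw change | t-test, log change | Adjusted log model | Adjusted minus rule |
|---|---|---|---|---|---|
| 0.6 | 0.4 | 70.5% | 84.4% | 94.1% | 23.6 |
| 0.6 | 0.6 | 85.1% | 95.1% | 98.0% | 12.9 |
| 0.8 | 0.4 | 45.4% | 59.2% | 76.0% | 30.6 |
| 0.8 | 0.6 | 60.4% | 77.9% | 86.0% | 25.6 |
| 1.0 | 0.4 | 30.6% | 41.9% | 55.0% | 24.4 |
| 1.0 | 0.6 | 43.9% | 60.0% | 69.1% | 25.2 |

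The gap is about 13 to 31 points. Taking change on the log scale alone recovers about 10 to 18 of them. The simulated adjusted-model column sits within 3 points of the formula in the first table.

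**What drives the loss.** A linear model on ranks of the 12-month value, adjusted for baseline ranks, loses only about 1 to 4 points against the log model in these settings. Adjustment therefore recovers nearly all the power even without a log transformation.

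**Type I error.** Rejection under no effect is 4.8% to 5.6% for all methods.

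**Wider range.** With the effect set so that the adjusted log model has about 80% power, the gap to rank-sum on 12-month values is about 1 to 2 points at correlation 0, 5 to 6 at 0.3, 13 at 0.5, 30 at 0.7 and 42 to 45 at 0.8. For rank-sum on raw change it runs the other way: about 27 points at correlation 0, falling to 6 to 11 at 0.8.

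**The case against.** The strongest reply is that the figures describe a plan the documents do not contain. They name paired tests, not rank-sum; they never mention change; they name no normality test; and they give no variance, correlation or effect for any marker. All of that is true, so both readings are shown as conditional ranges. What stands regardless is that neither reading adjusts for baseline and neither comes with a planned estimate.

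The other points limit the claim:

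- A reader might infer that ranking on the raw scale causes the 13 to 31 point loss. It does not. Ranks of 12-month values are identical on raw and log scales. The upper range applies only if raw change is analysed, where scale does matter.
- A reader might infer that normality is re-checked in the per-protocol set and in boys and girls, so that one outcome could receive different tests. The text allows this but does not say it; each variable could be classified once.
- A reader might infer that a rank test cannot give an effect size. A Hodges-Lehmann shift with interval is available. The missing estimate is an omission in the plan, and it affects the t-test branch equally.
- Most of the skewed markers are explanatory, the lowest tier, and calprotectin will not reach 42 per arm. This lowers the stakes.
- Correcting the paired-test fault rewrites the same sentence. The two changes should be made together, but substituting independent-sample tests alone would leave this point open.

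**Conclusion.** The point holds as a should-fix. The sentence leaves the choice of test to an unspecified normality judgement, makes no use of the baseline in the between-arm comparison, and plans no LA versus OA estimate with confidence interval.

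Under the assumed inputs, the cost is about 5 to 21 points of power if 12-month values are compared and about 13 to 31 if raw change is compared. Outside those inputs it can be as little as 1 point or more than 40. The figures are illustrations, not properties of the documents. No inflation of false positives is shown, and the primary analysis is untouched.

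**What to change.** In section 9 of both documents, replace the sentence with one method, fixed before unblinding and used in every analysis set:

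- Compare the 12-month value between arms in a linear model adjusted for the baseline value of the same outcome.
- Log-transform positive, skewed concentrations that are not already supplied on a log scale (such as lipid mediators, 8-iso-prostane, calprotectin, liver enzymes and CRP), naming them in advance. Report the ratio of geometric means, LA to OA, with 95% CI.
- Analyse other continuous outcomes, such as FEV1 % predicted, untransformed. Report the mean difference with 95% CI.
- Use no normality test to choose the method. Keep a rank-based test only for assays with many undetectable values.

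The cost is new wording and a few lines of code; no extra data are needed. The small downsides are that skewed markers are reported as ratios and that assays with many undetectable values need the stated exception.
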